### 5.1.3.9 Anemia

Anemia is present in the vast majority of patients with ESRD and is caused primarily by an inadequate production of endogenous erythropoietin (EPO), although recent evidence suggests an additional component of EPO resistance reflecting a state of chronic inflammation. While debate continues over the appropriate target hemoglobin, partial correction of anemia in ESRD patients has been associated with lower rates of mortality [Ma, 1999] hospitalizations [Xia, 1999], and cognitive and brain function [Pickett, 1999] in observational studies, and improved quality of life [Evans, 1990] in randomized controlled trials of EPO.

The effect of daily HD on anemia is not clear. Some observational studies have shown that daily HD improves anemia, resulting in higher hemoglobin levels at a fixed or lower EPO dose, or a stable hemoglobin, but at a lower EPO dose [Andre, 2002a;Fagugli, 1998;Klarenbach, 2002;Koshikawa, 2003;Ting, 2003;Traeger, 2004;Woods, 1999], while others have reported no significant effect [Fagugli, 2001;Piccoli, 2003;Pinciaroli, 1999;Rao, 2003;Ting, 2003;Vos, 2001;Woods, 1999]. Whether any improvements in anemia were masked by increased blood losses in these later studies is not known. In this trial, parameters related to anemia and iron use will be closely tracked, including hemoglobin, erythropoietin dose and route of administration, ferritin, transferrin saturation, and iron FHN Daily Protocol Version 2.3.1: July 2, 2008

utilization. The secondary outcomes related to anemia will be the 12 month change in hemoglobin, and the 12 month change in EPO dose. Outcomes related to iron status are described in Section 5.2.

# 5.2 Potential Risks of Daily HD

Prior observational studies of daily HD suggest overall benefit with no increased risk. However, these studies may have been inadequately powered to detect potential complications.

# 5.2.1 Vascular Access Complications

A theoretical risk of daily HD is that of increased vascular access failure due to twice as many access usages per week. Some studies suggest that this may be a risk for arteriovenous fistulae [Ting, 2003;Lindsay, 2003b], while others suggest that rates of access infection, stenosis and thrombosis may decrease with daily HD [Twardowski, 1999;Quintaliani, 2000;Woods, 1999;Lindsay, 2003b]. Access infections, interventions, and failures will be defined in the Manual of Operations, and will be monitored closely in both groups. Treatment groups will be compared with respect to: time to first access intervention, number of access interventions per patient year, time to first access failures, number of access failures per patient year, and number of infection related access failures per patient year.

# 5.2.2 Iron Losses

Patients on daily HD have been shown to have increased iron losses compared with conventional patients [Rao, 2003]. Cumulative monthly iron utilization will be compared between both groups, along with the 12 month change in transferrin saturation and in ferritin.

# 5.2.3 Malnutrition and Water Soluble Vitamin Deficiency

Although it is anticipated that nutritional status will improve with daily HD, the potential for malnutrition exists. There may be increased dialytic losses of amino acids due to increased clearances provided with daily HD. In addition, patients may miss more meals with daily HD, especially if their mealtimes coincide with their dialysis treatments or their travel to and from the dialysis unit. Nutritional status is being monitored as described in Section 5.1.3.5.

# 5.3 Assessment of Treatment Burden

Compared to conventional HD, the daily HD intervention may have increased treatment burden, due to the need for patients to travel to the dialysis unit twice as often. This may be reflected by decreased adherence to the daily therapy, as discussed above.

The patient's perception of burden will also be assessed using the question, "How long does it take you to recover from a dialysis session?" which was validated in the London study [Heidenheim, FHN Daily Protocol Version 2.3.1: July 2, 2008 36

2003]. This question was successfully answered on 313 of 314 occasions, and was directly correlated with subscales evaluating fatigue, disease stress, and psychosocial stress; and was negatively correlated with the SF-36 physical and mental component summary scores (unpublished data). This question was shown to be responsive, as significant reductions in recovery time were found when patients switched from conventional to either daily or nocturnal HD [Heidenheim, 2003].

### 6. Data Collection

### 6.1 Frequency of Measurements

The frequency of measurements is summarized in Table 11 below.

Most questionnaires (including HRQL, depression, cognitive function, and treatment burden) and objective tests of physical function will be performed at baseline, and at 4 and 12 months post-randomization. The purpose of the 4-month assessment is to allow evaluation of short-term effects prior to significant attrition, while the 12-month assessment is intended to allow evaluation of longer-term effects. The cardiac cine-MRI, and Holter monitor for heart rate variability will be performed at baseline and 12 months only. Bioelectric impedance should be performed at 1 month post-randomization in addition to baseline, 4, and 12 months. The purpose of the additional 1-month assessment is to elucidate early effects of the therapy on volume status.

Kinetic modeling sessions will be performed twice in the baseline period and monthly after randomization through month 12. Kinetic modeling parameters, including information on the dialysis prescription and the pre- and post-dialysis concentrations of urea, creatinine, and phosphate, as well as pre-dialysis albumin will be obtained at each session, while other labs will be collected less frequently (see Table 10 B). The pre and post-dialysis blood pressures, post-dialysis weight, and the presence of intradialytic hypotensive episodes will also be obtained for the kinetic modeling session. Once during baseline and monthly during follow-up, start and end times, pre- and postdialysis blood pressures, and pre- and postdialysis weights will be retrospectively obtained for the one-week interval preceding the modeling session, generally including two additional dialyses (for a total of three dialyses, including the modeling session) in daily patients. In addition, information on the dialysis prescription (but not local laboratory measurements) will be recorded for quality control for one of the dialyses during the second week follow-up randomization.

The frequency of local laboratory measures other than those described above for basic kinetic modeling will depend on the frequency with which they are performed at the various Clinical Centers, and should follow DOQI clinical practice guidelines. Locally performed pre-dialysis hemoglobin, calcium, bicarbonate, potassium, and sodium should be recorded at baseline and at least once per month post-randomization, while ferritin, transferrin saturation, and parathyroid hormone should be recorded at baseline and at least once every 4 months. Only baseline values done within 3 months before randomization will be used for any analysis.

All prescribed medications will be recorded at baseline and at months 4, 8, and 12 during follow-up, except for intravenous iron, which will be recorded at baseline and then monthly thereafter. The reason anemia medications will be recorded monthly is because of the frequency with which prescriptions and doses of these medications are changed.

Adherence to therapy will be obtained at baseline and on a monthly basis. All events, such has hospitalizations, deaths, access procedures, and discontinuations will be monitored continuously throughout follow-up.

The two baseline kinetic modeling sessions are designated as the B1 and B2 visits. The follow-up visits are designated as F1 (month 1), F2 (month 2), and so on through the F12 visit. However, if assessments that are designated for a specific visit window are missed during that window, attempts should be made to perform them during the following visit window.

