#### **Executive Summary**

The prevalence of end-stage renal disease (ESRD) is increasing, the cost of renal replacement therapy is high, and the disease and treatment are associated with significant mortality and loss in patient quality of life. Recent physiologic and observational studies have suggested improvements with more frequent hemodialysis (HD) regimens (daily or nocturnal HD).

Because no randomized trials of daily dialysis have been conducted, the first calendar year of the trial has been designated as a "Vanguard" phase during which feasibility of randomization and conduct of the interventions will be evaluated. If pre-defined benchmarks for establishment of feasibility are achieved during the Vanguard phase, the trial will proceed to its primary objective of determining if in-center daily HD improves physiological, health-related quality of life (HRQL) and functional outcomes, as compared with in-center conventional HD. The target sample size for this multi-center, randomized controlled trial is 250 subjects. Finally, this trial will evaluate costs and estimate cost-effectiveness of in-center daily HD.

Using broad inclusion criteria, subjects will be recruited from dialysis units affiliated with Clinical Centers in the United States and Canada and treated and followed for 1 year. Daily HD will be delivered for 1.5 - 2.75 hours, 6 days per week, while conventional HD will be delivered for at least 2.5 hours (typically 3 to 4 hours), 3 days per week. In the daily HD group dialysis prescriptions will target an eKt/Vn of 0.9 at each of the 6 weekly dialysis sessions. In the conventional HD group subjects will remain on their usual dialysis prescriptions subject to a minimum prescribed eKt/V of 1.1. Based on simulation studies the projected median weekly standard Kt/V is 3.82 in the daily HD arm and 2.46 in the conventional HD arm. The projected median weekly treatment time is 14.2 hours in the daily-HD arm and 10.5 hours in the conventional HD arm. Because the intervention, by necessity, is unblinded, efforts will be made to control bias. These include the use of objective outcomes, and efforts to standardize the use of co-interventions in both arms of the study.

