# 3.1.2 Rationale for Choosing Target Doses

# a) Conventional HD Group

HD dosing is traditionally based on clearance of urea, quantified as the Kt/V (K is the clearance of urea, t is time of dialysis session, and V is the volume of distribution of urea in the patient). Traditionally the single-pool Kt/V (spKt/V) has been used to define and measure dose in conventional HD [Gotch, 1985]. However, because the spKt/V overestimates true clearance due to the phenomenon of urea rebound, this trial will use equilibrated Kt/V (eKt/V) [Daugirdas, 1995;Pedrini, 1988]. In order to assure adherence to current national standards, a minimum eKt/V of 1.10 will be required in the conventional HD group. However, consistent with its designation as a conventional therapy arm, the dialysis prescriptions in the conventional HD group will be otherwise unspecified (subject to a minimum treatment time of 2.5 hrs).

Parameter	Conventional HD (CHD)	Daily HD (DHD)	% Difference in Medians (DHD vs. CHD)
Sessions per week	3	6	100%
Target prescription	Unspecified: $eKt/V \ge 1.10$	$eKt/(V_n) = 0.90$	-
Hours per session	$\geq 2.5$ (median = 3.50)	1.50 to 2.75 (median = 2.36)	-33%
Maximum interdialysis interval (median, hours)	68.5	45.6	-33%
Average interdialysis interval (median, hours)	52.5	25.6	-51%
Hours per week	10.5	14.2	2514
(median, $5^{th} - 95^{th}$ percentile)	(9.0-13.1)	(11.5 – 16.5)	+35%
eKt/V urea per treatment	1.39	0.92	2.40/
(median, $5^{th} - 95^{th}$ percentile)	(1.12 – 1.75)	(0.74 – 1.05)	-34%
Weekly stdKt/V urea	2.46	3.82	. 550/
(median, $5^{th} - 95^{th}$ percentile)	(2.16 – 2.80)	(3.32 – 4.17)	+55%
Weekly eKR $\beta_2$ -microglobulin (ml/min per 35 L total urea volume) (median, 5 th – 95 th percentile)	4.80 (3.77 – 6.21)	5.43 (4.26 – 6.85)	+13%
Standardized phosphorus removal (mg/day) (median, 5 th – 95 th percentile)	299 (254 - 374)	415 (338 – 497)	+39%

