#### 3.1.4 Data Collection, Determining the Initial Prescription, and Monitoring of Dose

Data to be obtained at kinetic modeling sessions are summarized in Table 6. Although kinetic modeling data will be obtained monthly in order to characterize the interventions, the protocol for establishing and updating dialysis prescriptions is designed to minimize the number of prescription modifications. The protocol for measurement of residual renal function is described in Section 3.1.5.

Treatment date
Start and end times (recorded)
Actual treatment time recorded on the dialysis machine, if available
Dialysate flow
Blood flow
Dialyzer membrane type
Reuse number
Interruption status (was total interruption time >15 min?)
Intradialysis hypotensive episodes and other symptoms requiring saline or reduced UF
Pre and Post HD systolic and diastolic blood pressure
Pre and Post HD weight
Pre and Post HD urea (local laboratory measurement)
Pre and post HD creatinine (local laboratory measurement)
Pre and post HD phosphate (local laboratory measurement)
Predialysis serum $\beta_2$ -microglobulin (to be measured in reposited serum specimens)
Predialysis serum albumin (local laboratory measurement)

\* In addition to data collection from the kinetic modeling session itself, start and end times, pre and post HD weights, predialysis blood pressures, and intradialytic hypotensive episodes leading to treatment interruptions will also be obtained from the dialysis run sheet for all HD sessions during the week preceding the kinetic modeling session once during baseline and monthly during follow-up.

a) Baseline Kinetic Modelling Sessions

Two kinetic modelling sessions, designated B1 and B2, will be conducted during the baseline evaluation phase of the trial. The two sessions will be spaced at least one week but no more than six weeks apart.

If the coefficient of variation of the estimates of urea distribution volume (V) from the two baseline kinetic modeling sessions (B1 and B2) differs by 20% or more, a third baseline kinetic modeling session (labeled B3) will be required. The median of all baseline urea volume estimates will be used to determine the initial post-randomization dialysis prescription.

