Intradialytic Hypotension: Intradialytic hypotensive episodes (IDHE) occur in approximately 20% of standard 3x/week dialysis treatments [Kyriazis, 2004]. In addition to complicating delivery of an adequate treatment and reducing patients' quality of life, repeated IDHE may cause ischemia to critical body organs, including brain, heart, intestines, and thereby contribute to an increased risk of hospitalization and death [Ishida, 1999]. IDHE has been associated with mortality in HD patients [Shoji, 2004;Tisler, 2003]. Due to a shorter interdialytic interval, daily HD results in lower ultrafiltration rates provided total daily fluid intake remains constant or minimally increased. It is thus hypothesized that daily HD will reduce the rate of IDHE, as suggested by some observational studies [Heidenheim, 2003].

Interdialytic Weight Gain: Absolute interdialytic weight gains correlate with pre-dialysis blood pressure. A decrease in interdialytic weight gain has been hypothesized to be one mechanism by which LVMi and blood pressure may improve. In previous observational studies, absolute weight gains between dialysis sessions have decreased with daily HD due to halving of the interdialytic interval, but in fact cumulative weekly gains have tended to increase [Andre, 2002b;Fagugli, 2001;Galland, 2004a;Kooistra, 1998;Nesrallah, 2003;Ting, 2003]. Thus, in this trial, both the 12-month changes in mean interdialytic weight gain between dialysis sessions, as well as in cumulative weekly weight gains will be assessed as additional secondary outcomes.

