# 6.2.7 Blood Pressure, Interdialytic Weight Gains, and Intradialytic Hypotensive Episodes

Pre and post-dialysis systolic and diastolic blood pressures, the nadir recorded intradialytic systolic and diastolic blood pressures, pre and postdialysis weights, and the presence of intradialytic hypotension requiring intravenous saline will be recorded from the HD run sheets for each HD session over a 1-week interval prior to and including the kinetic modeling session once during baseline and monthly during follow-up. In other words, these measures will be recorded for 3 sessions in the conventional arm, and at most for 6 sessions in the daily arm. Interdialytic weight gains will be calculated from the pre and post weights. See Table 11 C.

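### Section 6.1 counts three dialyses in a daily patient's recording week, contradicting the six-session schedule, its own one-week interval, Section 6.2.7 and Table 6

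*Protocol*

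**What the plan says.** Four places in the protocol describe the same monthly run-sheet abstraction.

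- Section 6.1 sets the period: the data "will be retrospectively obtained for the one-week interval preceding the modeling session". It then describes that week as generally adding two sessions to the modeling session, "for a total of three dialyses, including the modeling session) in daily patients".
- Section 6.2.7 asks for each session in the week up to and including the modeling session and spells out the count by arm: "these measures will be recorded for 3 sessions in the conventional arm, and at most for 6 sessions in the daily arm".
- The Table 6 footnote in Section 3.1.4 says that the run-sheet items "will also be obtained from the dialysis run sheet for all HD sessions during the week preceding the kinetic modeling session".
- The footnote to Table 11C refers to sessions over the prior one-week interval and gives no count.

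The daily schedule is not in doubt. The Executive Summary states: "Daily HD will be delivered for 1.5 - 2.75 hours, 6 days per week".

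The data feed named outcomes. Section 5.1.3.8 lists four key hypertension outcomes, three of which use the weekly average predialysis systolic pressure. Section 5.1.3.1 adds mean interdialytic weight gain and says that changes in it, "as well as in cumulative weekly weight gains will be assessed as additional secondary outcomes".

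**The concern.** Section 6.1 contradicts itself, because a week in a daily patient holds six sessions, not three. It also contradicts Section 6.2.7 and Table 6. The sentence tells sites what to abstract, so it is more than background text. Sessions that are never abstracted cannot be restored later by an analysis plan.

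The conflict is not symmetric. In the conventional arm, three sessions are the whole week under either reading. In the daily arm, three sessions are half of it. Any loss would therefore fall on one arm only, and only after randomization, since everyone is on three sessions a week at baseline.

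The protocol itself makes the choice of sessions matter. Section 5.1.3.8 warns that a comparison of six with three sessions a week can change with the timing of the pressure readings relative to dialysis. Section 5.1.3.1 notes that earlier studies tended to see cumulative weekly weight gain rise on daily dialysis, so an undercount in that arm could hide such a rise.

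**Working it through.** **Inputs.** Sessions per week: 6 daily, 3 conventional. Median session length from Table 3: 2.36 h daily, 3.50 h conventional. A week is 168 h. The longest start-to-start interval is taken as 48 h (daily) and 72 h (conventional).

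**Reproducing Table 3.**

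| Quantity | Formula | Daily | Conventional | Table 3 |
|---|---|---|---|---|
| Weekly hours | sessions × length | 6 × 2.36 = 14.16 | 3 × 3.50 = 10.5 | 14.2 / 10.5 |
| Average gap (h) | 168/sessions − length | 28 − 2.36 = 25.64 | 56 − 3.50 = 52.5 | 25.6 / 52.5 |
| Maximum gap (h) | longest interval − length | 48 − 2.36 = 45.64 | 72 − 3.50 = 68.5 | 45.6 / 68.5 |

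The table is reproduced, so a full daily week has five short gaps of 24 − 2.36 = 21.64 h and one long gap of 45.64 h. Total gap time is 5 × 21.64 + 45.64 = 153.84 h.

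**Three consecutive sessions instead of six, daily arm.**

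- Treatment time: 3 × 2.36 = 7.08 h, which is 50% of 14.16 h and below the conventional arm's 10.5 h.
- Weight gain, counting the gap before each recorded session and taking gain as proportional to gap length:
  - without the long gap, 3 × 21.64 = 64.92 h, and 64.92/153.84 = 42%;
  - with it, 2 × 21.64 + 45.64 = 88.92 h, and 88.92/153.84 = 58%.
- If only gaps between two recorded sessions can be used, the shares are 43.28/153.84 = 28% and 67.28/153.84 = 44%. Under that rule a three-session conventional record also loses a gap, so these shares do not measure the difference between arms.

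**Blood pressure average.** Suppose the session after the long gap runs D mmHg above the others, whose mean is m. The six-session mean is m + D/6. The three-session mean is m if that session is left out and m + D/3 if it is included. The difference from the full week is −D/6 or +D/6. The protocol gives no value for D. For an assumed D of 3, 5 or 10 mmHg, the shift is 0.5, 0.8 or 1.7 mmHg. Its sign depends on where the modeling session falls in the week, which Section 6.1 does not fix.

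**Conventional arm.** Three of three sessions under every reading, so nothing changes.

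**The case against.** The best reply is that Section 6.1 does not really tell sites to record three sessions. Its operative term is the one-week interval; the count is a gloss, softened by *generally*. Two sessions plus the modeling session is exactly the thrice-weekly pattern, so naming daily patients looks like a slip. Section 5.1.3.8 sends the reader to Section 6.2 for blood pressure details, which makes 6.2.7 the natural governing text, and Tables 6 and 11C agree with it. Section 9.9 also promises monitoring and feedback on missing data.

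Most of this stands. It makes the intended meaning fairly clear and makes harm less likely. It does not remove the contradiction: the sentence is intact, it names the wrong arm for that count, and it sits in the section a coordinator would consult for what to collect and when.

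The objection is also right on size. The halving applies to unscaled sums, and the protocol gives no such formula; scaling by sessions per week would remove most of it. Scaling would not correct which sessions enter the pressure average. Weekly treatment time describes the intervention and is not a listed outcome in Table 10.

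A reader might go further and infer that the trial deliberately samples half of the daily week, or that its weekly results are biased in favor of one arm. The documents support neither. Nothing suggests a design choice, nothing shows that sites followed the parenthesis, and the direction of any pressure shift is open.

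**Conclusion.** The point holds as an internal contradiction in a data-collection instruction, with a conditional consequence. If a site followed the count in Section 6.1, it would record half of the daily-arm sessions during follow-up and all of the conventional-arm sessions.

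- Session counts and summed treatment hours would be exactly half. Summed weight gain would be about half, under the proportional-gain assumption and with three consecutive sessions taken. Both statements concern sums that are not rescaled.
- The weekly blood pressure average would not be halved. It would shift by D/6 in either direction, with D not given in the documents.
- The outcomes exposed are the weekly blood pressure measures and cumulative weekly weight gain. Neither co-primary outcome nor any of the seven main secondary outcomes uses these weekly data.

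The correction should be made because it costs almost nothing, but the contradiction does not threaten the trial's main conclusions.

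**What to change.** Replace the parenthetical count in Section 6.1 with an instruction to record every session in the one-week interval: three in conventional patients, up to six in daily patients. That brings it into line with Section 6.2.7 and the Table 6 footnote. Send sites a short note saying so.

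The cost is one sentence and one notice; the run sheets already exist. No rule restricting weekly totals to fully recorded weeks is needed here. That is an analysis choice that can be left to the SAP, and it would tend to discard more daily-arm weeks, since a six-session week is more easily incomplete than a three-session one.

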### **B.** Laboratory Measurements and Medications

Measurement	Baseline	1 mo	2 mo	3 mo	4 mo	5 mo	6 mo	7 mo	8 mo	9 mo	10 mo	11 mo	12 mo
Predialysis serum albumin	~~	~	~	~	~	~	~	~	~	~	~	~	✓
Pre and post-dialysis serum phosphate, creatinine, urea	~~	~	~	~	~	~	~	~	~	~	~	~	√
Interdialytic urine for urea, creatinine, phosphate	~				~								√
Pre-dialysis hemoglobin, calcium, bicarbonate, sodium, and potassium	~	~	~	~	~	~	~	~	~	~	~	~	✓
Pre-dialysis transferrin and ferritin 	~			✓				✓				✓	
Pre-dialysis parathyroid hormone 	~			√				✓				✓	
Intravenous iron (cumulative monthly dose)	~	~	~	~	✓	~	~	~	~	~	~	~	~
Erythropoietin/Darbopoetin (route, frequency, weekly dose, cumulative monthly dose)	V				~				✓				~
IV vitamin D metabolites (frequency, weekly dose)	~				✓				~				~
Phosphorus binders (daily dose)	✓				~				~				✓
All other medications (including antihypertensives)	~				✓				~				✓
Serum/plasma samples for biorepository	~				~								~

These local labs to be entered into database at least once every 4 months (center may optionally enter these labs at additional time points) FHN Daily Protocol Version 2.3.1: July 2, 2008 40

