# 6.2.4 Medications

Study coordinators will verify that the medications correspond to the prescribed medication list prior to data collection and entry. All prescribed medications (except intravenous iron, erythropoeitin/darbopoetin, and intravenous vitamin D metabolites) will be recorded with daily doses using the WHO DRUG system at baseline and at the F4, F8, and F12 visits. For vitamin D metabolites, the frequency and total weekly dose will be recorded. For erythropoeitin/darbopoeitin, the frequency and total weekly dose, along with the cumulative dose over the last 4 weeks will be recorded. Intravenous iron use will be recorded monthly, as the cumulative dose over the prior 4 weeks. Please see Table 11 B.

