### 9.5 General Analytic Strategy for Quantitative Outcomes

The following analytic strategy will be employed for quantitative outcomes, including each of the main secondary outcomes with the exception of the rate of nonaccess hospitalization or death. The main analysis for each outcome will evaluate the treatment effect on the change from baseline to 1 year. For outcomes evaluated monthly (e.g., serum albumin and pre-dialysis phosphorus), the baseline value will be averaged over two baseline assessments and the 1 year value will be averaged over the Month 10, 11, and 12 assessments for increased statistical power. For each outcome with multiple follow-up assessments (including the PHC, serum albumin, Beck Depression Inventory, Trail Making Test B, and pre-dialysis phosphorus), an additional analysis will be conducted to evaluate the change from baseline to Month 4, where the Month 4 value is taken as the average value over months 3, 4, and 5 for serum albumin and pre-dialysis phosphorus. The analysis of change to 4 months will evaluate short term effects, while the analysis of change to 1 year will evaluate longer-term effects. The 4-month comparison is also intended to evaluate treatment effects prior to significant attrition. The "basic model" to be used for quantitative outcomes is:

$$\Delta Y_{t} = \beta_{0t} + \beta_{1t} \operatorname{Trt} + \beta_{2t} Y_{0} + \Sigma \gamma_{it} S_{i} + \Sigma \delta_{it} F_{i} + \varepsilon_{t}, \qquad (Basic Model)$$

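### Section 6.1 justifies monthly recording of anemia medications by frequent dose changes, but only intravenous iron is recorded monthly, so the 12-month EPO-dose value rests on a single 4-week window

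*Protocol*

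**What the plan says.** Section 6.1 first sets the general rule: "All prescribed medications will be recorded at baseline and at months 4, 8, and 12 during follow-up, except for intravenous iron", which is recorded at baseline and then every month. The next sentence gives the reason, but for a wider class of drugs: "The reason anemia medications will be recorded monthly is because of the frequency with which prescriptions and doses of these medications are changed".

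Table 11B ticks intravenous iron at baseline and at each of months 1 to 12. The row for EPO, whose listed items include a cumulative monthly dose, is ticked at baseline and months 4, 8 and 12 only.

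Section 6.2.4 takes EPO out of the general daily-dose list and says that "the frequency and total weekly dose, along with the cumulative dose over the last 4 weeks will be recorded". It gives EPO no frequency of its own and refers to Table 11B. It uses the word monthly for one drug only: "Intravenous iron use will be recorded monthly, as the cumulative dose over the prior 4 weeks".

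Section 5.1.3.9 names two secondary outcomes for the anemia domain, the 12-month change in hemoglobin "and the 12 month change in EPO dose", and says that parameters including EPO dose will be tracked closely. Section 9.5 provides, for outcomes evaluated monthly, that "the 1 year value will be averaged over the Month 10, 11, and 12 assessments for increased statistical power". Section 8.4(b) lists EPO dose and rate of EPO use among the potentially sensitive cost parameters. For injectable medicines, Table 13 says only that recording takes place at multiple time points.

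**The concern.** The reason given in 6.1 applies at least as well to EPO as to iron, and EPO is the anemia drug whose dose is a trial outcome. Yet EPO is left on the sparse schedule.

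Two uses of the data are affected. First, hemoglobin is collected monthly and so qualifies for the month 10–12 average, while EPO dose does not. Section 5.1.1 explains that the anemia domain has no single main outcome because a target hemoglobin may be held by changing erythropoietin. The two outcomes therefore have to be read together, and one would be a three-month average and the other a single window. Second, the economic analysis treats EPO use as an input that may drive the result, and section 8.4(c) plans separate cost estimates for the first and the last four months. Under the present schedule each of those periods contains one 4-week EPO record.

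**Working it through.** The protocol gives no power, variance or correlation figure for EPO dose, so there is no stated number to reproduce. The check has three parts.

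**1. Consistency of the schedule**

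| Place | Intravenous iron | EPO/darbepoetin |
|---|---|---|
| 6.1, schedule sentence | monthly (the only exception) | baseline, 4, 8, 12 |
| 6.1, rationale sentence | monthly | monthly, if anemia medications includes EPO |
| Table 11B | baseline and months 1–12 | baseline, 4, 8, 12 |
| 6.2.4 | monthly | no frequency given; refers to Table 11B |

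The schedule agrees with itself. The rationale sentence is the odd one out.

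**2. Share of follow-up observed**

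Inputs: 4 weeks per cumulative dose (6.2.4); three follow-up recordings (Table 11B); 12 months of treatment (3.2), taken as 52 weeks.

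- As scheduled: 3 × 4 = 12 weeks; 12/52 = 23.1%.
- Recorded monthly: 12 × 4 = 48 weeks; 48/52 = 92.3%.

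**3. Precision of the 12-month value**

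Take unit variance for each monthly dose and one baseline window, and adjust for baseline as the basic model in 9.5 does. Compare month 12 alone with the mean of months 10, 11 and 12. The correlations are assumed.

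*Equal correlation r between any two months (compound symmetry).*

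- Month 12 alone: residual variance 1 − r².
- Mean of three: (1 + 2r)/3 − r².
- r = 0.5: 0.4167/0.75 = 0.556, a 44% reduction.
- r = 0.8: 0.2267/0.36 = 0.630, a 37% reduction.

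*Correlation decaying with time, r to the power of the gap in months (AR(1)).*

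- Month 12 alone: 1 − r²⁴.
- Mean of three: (3 + 4r + 2r²)/9 − [(r¹⁰ + r¹¹ + r¹²)/3]².

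| Monthly r | Month 12 alone | Mean of 10–12 | Ratio | Reduction |
|---|---|---|---|---|
| 0.5 | 1.000 | 0.611 | 0.611 | 39% |
| 0.8 | 0.995 | 0.823 | 0.827 | 17% |
| 0.9 | 0.920 | 0.814 | 0.885 | 12% |
| 0.95 | 0.708 | 0.632 | 0.893 | 11% |

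In standard-error terms (square root of the ratio), the gain is 21–25% in the first case and about 6–22% in the second.

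**The case against.** The strongest reply is that nothing is wrong with the schedule. The schedule sentence in 6.1 and Table 11B agree, and 6.2.4 says nothing different. The disputed sentence directly follows the iron exception and may simply explain it in loose wording. A site working from Table 11B would collect what the table intends, and narrowing one sentence would remove the contradiction. This stands as far as it goes: monthly EPO recording is the better repair, not the only one. But the plural wording fits iron alone poorly, and the narrow repair leaves the stated reason unapplied to the drug whose dose is an outcome.

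It is also fair that EPO dose carries limited weight. Anemia has no main endpoint (5.1.1, 9.4) and no power is claimed for it. The change score also uses a baseline window, months 4 and 8 are collected, the basic model fits months 4 and 12 jointly, and a 4-week cumulative dose already smooths short fluctuations. Other outcomes, such as the physical health composite, also rest on one 12-month assessment. These points limit the importance but do not restore the averaging.

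On costs, 8.4(b) already varies EPO dose and use in sensitivity analysis, and the comments to Table 13 plan a check against billed charges. That check covers only Medicare Primary patients and is described in connection with estimates from hospital-stay data.

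Three stronger readings are tempting, and the document supports none of them:

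- **Bias between arms.** A reader might infer that the treatment comparison is biased. Both arms share the same evenly spaced windows, and nothing in the protocol shows a bias.
- **Costs rest on 12 of 52 weeks.** Table 13 does not say that annual EPO cost is built from these three windows alone.
- **A gain of 37–44%.** That range needs the baseline-to-month-12 correlation to equal the month 11-to-12 correlation, which sits badly with doses that change often.

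**Conclusion.** The contradiction in 6.1 is real, and it has a modest consequence. The 12-month EPO value rests on one 4-week window, and the month 10–12 average is not available to it. The precision forgone is a residual variance reduction of about 37–44% under compound symmetry (r 0.5–0.8), or about 11–39% under AR(1) decay (monthly r 0.95–0.5). The protocol supplies no correlation, so neither range can be preferred from the document alone. If EPO costs come from the trial recordings, they sample about 23% of the year; that condition is an inference.

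The point concerns precision on a secondary outcome and on a cost input. It does not touch the co-primary endpoints or the seven main secondary endpoints. It merits a correction while data collection can still be changed, but it is no threat to the trial's main conclusions.

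**What to change.** Reconcile 6.1, 6.2.4 and Table 11B as follows:

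- In Table 11B and 6.2.4, record the 4-week cumulative EPO/darbepoetin dose every month alongside intravenous iron. The item is already defined; only its frequency changes.
- Analyse the 12-month EPO value as the mean of months 10, 11 and 12, as 9.5 does for albumin and phosphorus.
- State in section 8 that the monthly doses are used for the EPO cost.

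The cost is nine extra dose entries per patient (months 1, 2, 3, 5, 6, 7, 9, 10 and 11), so up to 9 × 250 = 2,250 entries in all, plus an amendment. No new visit or procedure is needed, because iron is already recorded at those months. The change is to data collection only and leaves treatment as it is.

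If the sponsor prefers to keep EPO at months 4, 8 and 12, it should limit the rationale sentence in 6.1 to intravenous iron and state how annual EPO cost is derived from the three windows.
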